## **2. STUDY OBJECTIVES**

### **2.1 Primary Objective**

To evaluate the effect of a high-fat meal on the PK of bexagliflozin extended release tablets in healthy subjects.

### **2.2 Secondary Objectives**

To evaluate the safety of bexagliflozin after a single oral dose in a fasted state and in a fed state in healthy subjects.

To evaluate the effect of a high-fat meal on the potential pharmacodynamic (PD) activity of bexagliflozin by determining urinary glucose excretion (UGE) in healthy subjects under fasted and fed conditions.

### 3. STUDY DESIGN

#### 3.1 Study Design

This single center, phase 1, open-label,  $2 \times 2$  crossover study is designed to assess the effects of a high-fat meal on the PK of orally administered bexagliflozin tablets. Eighteen (18) eligible healthy subjects will be randomized into two treatment groups such that an equal number ( $n = 9$ ) of subjects will receive a single oral dose of 20 mg of bexagliflozin with or without a meal on treatment day 1. Subjects randomized to receive bexagliflozin tablets with a high-fat meal on day 1 will receive a second dose of bexagliflozin tablets without a meal on treatment day 8 after an overnight fast. Subjects randomized to receive bexagliflozin tablets without a meal on treatment day 1 after an overnight fast will receive a second dose of bexagliflozin tablets with a high-fat meal on treatment day 8.

Bexagliflozin will be taken orally with 240 mL of water in the morning (approximately 8 a.m. to 10 a.m.). The time of dosing for a given subject will be the same (as far as practicalities permit) in both treatment periods.

The high-fat meal will follow the FDA guidance (Food and Drug Administration 2002) on high-fat (50% of total caloric content of the meal) and high-caloric (800 to 1000 calories) content. An example of the high-fat meal would be two eggs fried in butter, two strips of bacon, two slices of toast with butter, four ounces of hash brown potatoes and eight ounces of whole milk. Substitutions in this meal can be made as long as the meal provides a similar amount of calories from protein, carbohydrate, and fat and has comparable meal volume and viscosity.

Subjects dosed in the fed state will receive a 20 mg oral bexagliflozin tablet 30 min after starting to consume a high-fat meal after an overnight fast. No additional food should be allowed for at least 4 h post-dose. Water will be allowed as desired except for one hour before and after drug administration. The meal will be ingested in its entirety over an approximate 25-minute period, such that it is completed at least 5 minutes prior to the scheduled time of bexagliflozin dosing for the fed state treatment. If for some reason, a portion of the meal is not consumed, the reason and the amount of remaining food will be recorded. Subjects should receive standard meals at approximately the same time in each period of the study.

Subjects dosed in the fasting state will receive a 20 mg oral bexagliflozin tablet after an overnight fast. No food should be allowed for at least 4 h post-dose. Water will be allowed as desired except for one hour before and after drug administration. Subjects should receive standard meals at approximately the same time in each period of the study.

Subjects will be admitted to the clinic on day 0 and day 7, the day before dosing in each treatment period, and will stay in the clinic until 48-h post-dose. Standard meals will be served at the clinic during the stay. Blood samples (2 mL) for bexagliflozin plasma concentrations will be collected at 0 h (pre-dose), and at 1, 2, 3, 4, 5, 6, 8, 10, 12, 16, 24, 36, and 48 h post-dose (days 1-3 in treatment period 1 and days 8-10 in treatment period 2 respectively).

Urine collection in 12 h batches will be performed at pre-dose (-12 to 0 h on day 1 and day 8), and at post-dose at 0 to 12 h, 12 to 24 h, 24 to 36 h, and 36 to 48 h.

Clinical laboratory tests and safety monitoring will be conducted during both treatment periods.

### **3.2 Randomization**

A sufficient number of subjects will be screened to ensure that up to 18 subjects will be randomized. Eligible subjects will be randomly assigned to treatment group 1 or treatment group 2 in a 1:1 ratio. Subjects who discontinue the study after randomization for non-safety related reasons may be replaced to ensure that the number of evaluable subjects in each treatment group should not be less than 8.

### **3.3 Hypothesis Testing**

No formal statistical hypothesis testing will be conducted for this study.

### **3.4 Interim Analysis**

There will be no interim analysis conducted.

### **3.5 Sample Size**

For this Phase 1 food effect study, a sample size of 18 subjects is considered sufficient. The sample size for this study is not based upon formal statistical consideration. The sample size is considered adequate to characterize the PK of bexagliflozin, to assess potential food-drug interactions, and to provide safety and tolerability data on bexagliflozin when administered with food.

### **3.6 Schedule of Assessments and Study Procedures**

**Table 1. Schedule of Events**

Study activity	Screening		Period 1				Period 2				
	D -28 to -1	D0	D1 pre-dose	D1 post-dose	D2	D3	D7	D8 pre-dose	D8 post-dose	D9	D10
Medical history and ICF	X										
Screening for I/E criteria 	X	X					X				
Physical exam 	X	X									X
Demographics	X										
Randomization		X									
Admission and discharge		X				X	X				X
Vital signs 	X		X	X		X		X	X		X
ECG 	X		X	X				X	X		X
Urinalysis 	X		X			X		X			X
Blood draw for clinical lab tests 	X		X			X		X			X
Blood sample for PK 			X	X	X	X		X	X	X	X
Urine Collection 		X	X	X	X	X	X	X	X	X	X
Urine Pregnancy Test	X										
Adverse event and concomitant medication		X	X	X	X	X	X	X	X	X	X
Study termination											X

Abbreviations: D = day; ECG = electrocardiogram; ICF = informed consent form; I/E = inclusion/exclusion; PK = pharmacokinetic.

1. Subject compliance with inclusion and exclusion criteria will be verified at check-in of each period (on day 0 and day 7).
2. Weight and height will be recorded as part of the physical examination (PE). Height will be recorded once at screening only. A complete PE will be performed at screening and day 10 prior to discharge.
3. Vital signs include: pulse, body temperature, respiration rate, systolic and diastolic blood pressure (BP). On days 1 and 8, vital signs will be determined at pre-dose and at 4 h and 48 h (day 3 or 10) post-dose.
4. 12-lead electrocardiogram (ECG) will be conducted after 10 min of rest. ECG data will be recorded at screening, on days 1 and 8 at pre-dose and at 4 h post-dose, and when clinically indicated.
5. Clean sample to be collected at each visit. If urine is dipstick positive for leukocyte esterase or nitrites, sample is to be sent for microscopic evaluation and culture. Urine drug screen will be performed on screening visit only. If screening is conducted more than 5 days prior to dosing, drug screening shall be repeated.
6. Blood samples at the designated visits for clinical chemistry and hematology parameters are listed in [Table 2](#).
7. Plasma samples for the PK profile of bexagliflozin will be collected at pre-dose and at 1, 2, 3, 4, 5, 6, 8, 10, 12, 16, 24, 36, and 48 h post-dose.
8. Urine collection for urinary glucose (PD), electrolytes, uric acid & creatinine. Pre-dose urine samples will be collected from -12 to 0 h for baseline measurement. Post-dose urine will be collected in four batches: 0 to 12 h, 12 to 24 h, 24 to 36 h, and 36 to 48 h collections.

#### **4. DATA AND ANALYTICAL QUALITY ASSURANCE**

The overall quality assurance (QA) procedures for the study data, statistical programming and analyses are described in Everest's Standard Operating Procedures (SOPs). Detailed data management (DM) procedures are documented in the Data Management Plan, Data Validation Check Specifications, and Data Review Plan. Detailed statistical and programming quality control (QC) and QA procedures are documented in the Statistical Analysis and Programming QC/QA Plan.

The study endpoints and analytic approaches are both prospectively defined and documented in the protocol and in this SAP. The SAP will be finalized, and protocol violations will be identified and decisions for inclusion and exclusion of subjects from the PK Population will be made prior to the database lock and data analysis.

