5.5 Blinding

This is an open-label study. There is no blinding process in this protocol.

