9 PLANNED STATISTICAL METHODS

9.1 General Considerations

The statistical evaluation of PK parameters will be conducted by the designated CRO. A detailed Statistical and Analytical Plan will be generated prior to initiation of the study. Statistical analysis will be performed using Statistical Analysis Software SAS for Windows[®] (SAS Institute Inc., USA). Non-compartmental analysis will be performed using Phoenix[®] WinNonlin[®] 6.4 (Certara, USA).

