##### **5.2 Pharmacokinetic Population**

The PK Population will include all randomized subjects who receive study drug and who have sufficient plasma bexagliflozin measurements to derive at least one PK parameter following dosing. The PK Population will be used to summarize the PK parameters.

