## **7. PHARMACOKINETIC/PHARMACODYNAMIC ANALYSES**

### **7.1 General Considerations**

The PK Population will be used for PK analyses. The PD Population will be used for PD analyses.

Statistical and PK analyses will be performed by Everest Clinical Research. Statistical analysis will be performed using Statistical Analysis Software SAS for Windows® (SAS Institute Inc., USA). Non-compartmental analysis (NCA) will be performed using Phoenix® WinNonlin® 6.4 (Certara, USA).

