### **10. CHANGES FROM METHODS PLANNED IN THE PROTOCOL**

Any changes to methods planned in this statistical analysis plan will be documented in a revision to this statistical plan prior to database lock, or identified in the clinical study report.

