**14. APPENDIX 2 SAS CODE FOR STATISTICAL ANALYSES**

This section will be completed after examining the existing data and prior to the final signoff of this SAP.

Test	Table/Figure	SAS Codes for Modeling
ANOVA using a linear mixed-effects model.	PK endpoints requiring ANOVA.	
Analysis using PROC MIXED in SAS with SEQ, SUBJ, PERIOD, and TRTP identifying SEQUENCE, SUBJECT, PERIOD and TREATMENT variables. “Y” denotes the response measure (log (AUC), log (CMAX)). “KR” denotes Kenward-Roger method. “CL” denotes confidence limits.
 <pre> PROC MIXED METHOD=REML;   CLASS SUBJ SEQ PERIOD TRTP;   MODEL Y = SEQ PERIOD TRTP / DDFM=KR;   RANDOM SUBJ(SEQ);   LSMEANS TRTP / PDIF CL ALPHA = 0.10;   ESTIMATE 'T/R' TREAT -1 1 / CL ALPHA = 0.1; RUN; </pre> 
Anti-log transformation to obtain the geometric means. “GEO” denotes geometric and “LS” denotes least square.
 <pre> DATA LSMEANS;   SET LSMEAN;   GEOLSMEAN = EXP(ESTIMATE); RUN; </pre> 
Anti-log transformation to obtain the ratio of geometric means (point estimate) and 90% confidence interval (CI) – lower and upper bounds.
 <pre> DATA DIFFS;   SET ESTIMATE;   RATIO = EXP(ESTIMATE)*100;   LOWER = EXP(LOWER)*100;   UPPER = EXP(UPPER) * 100; RUN; </pre>

**15. APPENDIX 3 REFERENCE RANGES AND CLINICALLY RELEVANT CHANGES  
FROM BASELINE FOR MARKED LABORATORY ABNORMALITIES**

<To be inserted>

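### Does the SAP leave PK Population exclusions open enough for a subject to be dropped because of how the fed:fasted AUC ratio would move?

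*SAP*

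**What the plan says.** SAP section 4 provides for a review in which "protocol violations will be identified and decisions for inclusion and exclusion of subjects from the PK Population will be made prior to the database lock". The sentence goes on to put that decision before the data analysis too. The same section states that "The study endpoints and analytic approaches are both prospectively defined and documented in the protocol and in this SAP" and refers to a Data Review Plan, which is not among the documents supplied.

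SAP section 5.2 and protocol section 9.3 define the PK Population identically: all randomized subjects who were dosed and who have "sufficient plasma bexagliflozin measurements to derive at least one PK parameter following dosing". Neither mentions violations.

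Four further places bear on the question:

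- Protocol 5.5: "This is an open-label study. There is no blinding process in this protocol".
- SAP 7.1: "Statistical and PK analyses will be performed by Everest Clinical Research".
- SAP Appendix 2, above the SAS code: "This section will be completed after examining the existing data and prior to the final signoff of this SAP". Protocol 9.1 says "A detailed Statistical and Analytical Plan will be generated prior to initiation of the study".
- SAP section 10 requires a change of method to be documented in a revised plan before lock "or identified in the clinical study report".

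The result is read from the 90% confidence interval for the fed:fasted ratio against 80-125% (SAP 7.2). SAP 3.3 states that no formal hypothesis test is planned.

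**The concern.** Section 4 ties exclusion to protocol violations, but the population definition names none. The deviation one would most expect in a food-effect study, an unfinished high-fat meal, is to be recorded (protocol 3.1 and 5.7.2) with no stated consequence for the analysis. Such an event affects one period, whereas section 4 speaks of subjects.

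Nor does the plan separate those who decide from the assay results. The section 5.2 test needs to know which concentrations are available. A subject's fed and fasted profiles side by side show which way that subject pulls the ratio, even before a model is run. The Appendix 2 sentence adds to the unease, because it suggests that data are looked at before the SAP is signed.

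With 18 subjects, one exclusion can carry the interval across a limit. If exclusions were chosen for their effect, the 5% chance of wrongly reading a lack of interaction at the boundary would not be held. AUC is where this could matter. Protocol 1.3 gives rounded AUC figures of 40 and 50 per mg before and after a meal, a ratio of 50/40 = 1.25, although protocol 3.2 reports no AUC effect with a standard meal.

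**Working it through.** **What the text allows.** Two steps are needed for a harmful exclusion: discretion to exclude, and knowledge of the result.

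- Discretion: section 5.2 starts from all randomized and dosed subjects and removes only those from whom no PK parameter can be derived. Section 4 says when membership is settled. It does not add a second criterion. Read together, they leave little to choose.
- Knowledge: section 4 puts the decision before both lock and analysis. Concentrations may be visible by then, but the plan does not have the ratio in hand at that point.

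**Size if someone did choose.** The plan states no CV, expected ratio or power, so there is no figure of its own to reproduce. Inputs are 9 + 9 subjects, a 90% interval and limits 0.80 and 1.25 (SAP 3.1 and 7.2). Assumptions are a within-subject CV of 15-30% and one to three subjects with a recorded violation but normal exposure.

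For log(fed/fasted) within a subject:

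- SD = sqrt(2 × ln(1 + CV²)). At CV 20% this is 0.280.
- The estimate is the average of the two sequence means. SE = SD × sqrt(1/9 + 1/9)/2 = 0.280 × 0.471/2 = 0.0660.
- With t(0.95, 16 df) = 1.746, the half-width is 0.115, a factor of exp(0.115) = 1.122.
- Dropping one of nine subjects who lies d from the sequence mean moves that mean by d/8 and the estimate by d/16. For d = 2 SD at CV 20%, the ratio moves by exp(0.560/16) = 1.036. Across CV 15-30% the factor runs from 1.027 to 1.053.

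Simulated share of trials with the 90% interval inside 80-125% at a true ratio of 1.25, where any subset of the violators may be dropped if that brings the interval inside the limits:

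| Rule | CV 15-30% |
|---|---|
| All 18 kept | about 5% |
| One optional violator | about 6% |
| Two | about 7% |
| Three | 8-9% |
| Any one of the 18 (worst case) | 13-14% |

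At a true ratio of 1.00 the lack-of-interaction reading is correct. A favourable choice then gains little over the full set: at CV 20%, from 89% to 90%, 91% and 93% with one, two and three violators.

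**Subject or period.** At CV 20%, dropping the whole pair gives SE = 0.280 × sqrt(1/8 + 1/9)/2 = 0.0680. Dropping only the fed period under the mixed model gives 0.0675-0.0678 (assumed between-subject CV 20-40%). The unit of exclusion hardly matters for precision.

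**Cmax.** At the smallest earlier food effect on Cmax, 1.39 (protocol 3.2), the interval falls inside the limits in at most 2% of trials even if any one subject may be dropped.

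**Appendix 2.** The model code is already written below the sentence, and it concerns code, not populations. It reads as a leftover from a template.

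**The case for a change.** The strongest case for a change is that timing is not separation. A decision made before lock can still be made with concentrations on the table, and the section 5.2 test requires some sight of them. If section 4 gives no discretion, a line saying so would cost nothing. If it does give discretion, the excluding violations should be listed. At a true ratio of 1.00 and CV 20%, the gap between the most and the least favourable choice is about 5, 11 and 19 percentage points for one, two and three violators.

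Part of this stands. No violation is named, access to concentrations is not described, and the word evaluable in SAP 3.2 is undefined. Listing criteria would be tidier, and if the Data Review Plan holds them a cross-reference would do.

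The rest does not carry. The 5, 11 and 19 points subtract one adversary from its opposite. No single analyst produces that difference, and the favourable side causes no error when the ratio truly is 1.00. Open-label status concerns knowledge of treatment, not access to assay data. A fixed sensitivity analysis would need cut-offs for leftover food or vomiting that are themselves debatable, and the figures favour neither set as primary: with one violator losing 25% of fed AUC at CV 20%, always keeping gives 87% inside the limits and always dropping gives 86%. Defining evaluable by section 5.2 would do harm, since a subject with one period would count. Selection of terminal points by visual inspection (SAP 7.2) would also stay a judgement made with concentrations in view.

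**Conclusion.** No change follows. The gap is one of detail: section 4 mentions violations and section 5.2 lists none. A sponsor who follows the text keeps every dosed subject with derivable PK, settles membership before lock and analysis, and reports an interval with its nominal 5% error at each limit. The by-subject listings of concentrations and PK parameters (SAP 7.2) would expose any unusual exclusion.

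If the gap were misused, the cost at a true AUC ratio of 1.25 would be about one percentage point with one optional violator and three to four points with three. That rests on an assumed CV of 15-30%, an assumed count of violators, and a decision-maker who knows and exploits the result, which the documents do not show. The Cmax reading would not be affected. The Appendix 2 sentence is most likely a clerical leftover.

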#### **5. ANALYSIS POPULATIONS**

Three subject populations will be evaluated during this study and are defined as follows:

##### **5.1 Safety Population**

The Safety Population will include all randomized subjects who receive at least one dose of the drug. Subjects will be analyzed according to the treatment received.

##### **5.2 Pharmacokinetic Population**

The PK Population will include all randomized subjects who receive study drug and who have sufficient plasma bexagliflozin measurements to derive at least one PK parameter following dosing. The PK Population will be used to summarize the PK parameters.

##### **5.3 Pharmacodynamic Population**

The PD Population will include all randomized subjects who have PD parameter data available in both treatment periods. The PD Population will be used to summarize the PD parameters.

#### **6. SPECIFICATION OF ENDPOINTS AND VARIABLES**

##### **6.1 Demographic and Baseline Characteristics**

Demographic variables consist of the following:

- Age in years (continuous) derived as the integer value of  $(\text{informed consent date} - \text{date of birth} + 1)/365.25$
- Sex
- Race
- Ethnicity

Baseline characteristics consist of the following:

- Weight (kg)
- Height (cm)
- Vital signs

- systolic blood pressure (SBP, mmHg)
- diastolic blood pressure (DBP, mmHg)
- oral temperature (°C)
- pulse (beats per minute)
- respiration rate
  
- Electrocardiogram (ECG) parameters
  - RR interval (msec)
  - PR interval (msec)
  - QRS duration (msec)
  - QT interval (msec)
  
- Medical and surgical history
- Clinical laboratory tests
- Prior and concomitant medication
- Physical examination

### 6.1.1 Study Day and Visit Window Definitions

**Table 2. Time Windows for Safety Assessments**

Time Windows for Safety Assessments			
Scheduled Visit Number	Visit (label)	Time Interval (day)	Target Time Point (day)
1	Screening	-28 to -1	-28 to -1
2	Day 1	1	1
3	Day 2	2	2
4	Day 3	3-6	3
5	Day 7	7	7
6	Day 8	8	8
7	Day 9	9	9
8	Day 10	10	10

Data obtained during unscheduled visits will be allocated to the scheduled visit corresponding to the visit window they fall in as specified in Section 6.1.1. Safety data obtained during unscheduled time points will be allocated to the scheduled time point corresponding to the time window in which they fall. Data will be analyzed based on the nominal visits and nominal time points. If the data from the nominal visit or time point is missing, data from unscheduled visits for the same nominal visit or time point will be used. If multiple unscheduled assessments fall in the same visit window or time point, the non-missing assessment closest to target time point will be selected for analysis.

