This is a phase 1, single center, open-label, 2 × 2 crossover study designed to assess the effects of a high-fat meal on the PK of orally administered bexagliflozin tablets, 20 mg. Following a ≥ 10-h overnight fast, eighteen (18) eligible healthy subjects will be assigned to two groups with an equal number (n=9) of subjects per group to receive a single oral dose of bexagliflozin tablets, 20 mg, in either a fasted state or 30 min after starting a high-fat meal. A washout period of at least 7 days will be used between the two treatment periods, after which, subjects will receive bexagliflozin tablets, 20 mg, in a fasted or fed state (high-fat), whichever state they had not received previously. The high-fat meal will be ingested in its entirety over an approximate 25-minute period, such that it is completed at least 5 minutes prior to the scheduled time of bexagliflozin dosing for the group receiving bexagliflozin with food. If a portion of the meal is not consumed, the reason and the amount of remaining food

will be recorded. No food should be allowed for at least 4 h after drug administration. Standard meals will be served to both groups 4 hour after dosing.

In treatment period 1, subjects will be admitted to the clinic on day 0, the day before dosing, and will stay in the clinic until 48-h post-dose. In treatment period 2, subjects will be admitted to the clinic on day 7, the day before dosing, and will stay in the clinic until 48-h post-dose. Blood samples for bexagliflozin plasma concentrations will be collected in each period at pre-dose and at 1, 2, 3, 4, 5, 6, 8, 10, 12, 16, 24, 36, and 48 h post-dose. Urine collection in 12 h batches will be performed at pre-dose (-12 to 0 h on day 0 and day 7), and at post-dose at 0 to 12 h, 12 to 24 h, 24 to 36 h, and 36 to 48 h.

Clinical laboratory tests and safety monitoring will be conducted during both treatment periods.

Study Population:

Eighteen healthy subjects are planned to be enrolled and dosed.

Diagnosis and Main Criteria for Inclusion

1. Healthy subjects who are between the ages of 18 and 65 years, inclusive.
2. Subjects with body-mass index (BMI) between 18.0 kg/m² and 32.0 kg/m², inclusive.
3. Male subjects who are surgically sterile or male subjects who are not surgically sterile but who agree to refrain from donating sperm and use appropriate birth control such as the use of condoms when engaging in sexual intercourse for a period of 30 days after discharge from the clinic.

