6.5 Electrocardiography and Continuous Telemetry Monitoring

6.5.1 12-Lead Electrocardiograms

A 12-lead electrocardiogram (ECG) will be conducted as listed in [Appendix 1](#) and whenever clinically indicated.

This procedure should be performed in the supine position after at least 10 min of rest. ECG parameters measured will be the RR interval, PR interval, QRS duration, and QT. Each ECG should also be assessed by the investigator for signs of ischemia, clinically significant hypertrophy, and clinically significant T-wave abnormalities.

It is the investigator or designee's responsibility to review the results of the ECG as they become available. For each abnormal ECG result, the investigator needs to ascertain if this is a clinically significant change from the screening ECG for that individual subject (this determination, however, does not necessarily need to be made the first time an abnormal result is observed. The investigator may repeat the ECG to verify the results of the original result). If the ECG result is determined to be a clinically significant and abnormal change from baseline for that subject, this is considered an AE.

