### **6.3.6 Electrocardiogram**

ECG parameters, including the RR interval (intra-beat interval), PR interval (the period that extends from the beginning of the P wave [the onset of atrial depolarization] until the beginning of the QRS complex [the onset of ventricular depolarization]), QRS duration, and QT interval (the corrected QT interval is the measure of the time between the start of the Q wave and the end of the T wave in the heart's electrical cycle), will be measured according to the study assessment schedule as specified in Section 3.6. Each ECG will be assessed by the Investigator for signs of ischemia, clinically significant hypertrophy, and clinically significant T-wave (repolarization of the ventricles) abnormalities. Baseline ECGs will be defined as the last evaluation performed prior to the administration of study drug in each treatment period.

ECG changes from baseline will be summarized by treatment.

Change from baseline to time point t, denoted  $\text{Change}_t$ , will be calculated as:

$$\text{Change}_t = \text{Value}_t - \text{Value}_{\text{Baseline}}$$

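### SAP Table 2 lets a value from as late as Day 6 stand as the 48-h vital-sign or laboratory reading in Period 1, while Period 2 allows one day only

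*SAP*

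**What the plan says.** SAP 6.1.1, Table 2 ("Time Windows for Safety Assessments"), is one run of windows in whole study days from Screening to Day 10. After screening every window is a single day, except Day 3, which covers Days 3-6 with Day 3 as target. Day 10 covers Day 10 only. These are the two 48-h visits. Footnote 3 of the Schedule of Events (SAP 3.6) states: "On days 1 and 8, vital signs will be determined at pre-dose and at 4 h and 48 h (day 3 or 10) post-dose".

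The text under Table 2 then sets four rules:

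- Unscheduled visits: "Data obtained during unscheduled visits will be allocated to the scheduled visit corresponding to the visit window they fall in".
- Unscheduled time points: "Safety data obtained during unscheduled time points will be allocated to the scheduled time point corresponding to the time window in which they fall".
- Scheduled data are analysed under their nominal visit and time point.
- Filling: "If the data from the nominal visit or time point is missing, data from unscheduled visits for the same nominal visit or time point" are used in its place. If several values qualify, the non-missing one nearest the target is taken.

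The values feed the by-treatment summaries of vital signs and laboratory tests, including change from baseline (SAP 6.3.5, 8.4.2 and 8.4.3). In the Schedule of Events, Period 1 has clinical laboratory draws and urinalysis before dosing on Day 1 and again on Day 3. Period 2 has them before dosing on Day 8 and again on Day 10.

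**The concern.** The 48-h reading should mean the same thing in both periods of a crossover. Under Table 2 it does not. In Period 2 only a Day 10 value can stand as the 48-h reading. In Period 1 a value taken up to three days after discharge can do so, and the SAP gives no reason for the difference.

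The summaries concerned serve the secondary safety objective. A value from Days 4-6 is taken outside the clinic stay, when the drug has essentially gone. Reporting it as a 48-h change from baseline would tend to pull that change towards zero. For laboratory tests the Day 3 draw is the whole of the scheduled post-dose information in Period 1, so its window decides what that period contributes.

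**Working it through.** The plan gives no figure to reproduce here, because this is an allocation rule. The check is to see which times after dosing the rule admits.

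**Inputs**

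- Windows: Day 3 = Days 3-6; Day 10 = Day 10 (SAP Table 2).
- Dosing at about 8 to 10 a.m. on Day 1 and Day 8 (SAP 3.1).
- Mean elimination half-life 7.80 to 9.71 h (Protocol section 1).
- 18 subjects, 9 per sequence (SAP 3.1).

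**Hours after dosing that each 48-h window admits**

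The end of study day d falls at (d − dosing day) × 24 + (24 − dosing hour).

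| Window | Start | End, 8 a.m. dose | End, 10 a.m. dose |
|---|---|---|---|
| Period 1, Days 3-6 | 38-40 h | 5 × 24 + 16 = 136 h | 5 × 24 + 14 = 134 h |
| Period 2, Day 10 | 38-40 h | 2 × 24 + 16 = 64 h | 2 × 24 + 14 = 62 h |

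At the same clock time as dosing, Days 4, 5 and 6 are 72, 96 and 120 h after dosing.

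**Drug exposure at those times**

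- 48 h: 48/9.71 = 4.9 to 48/7.80 = 6.2 half-lives. The fraction left, relative to the terminal phase at dosing, is 2^(−48/7.80) = 1.4% to 2^(−48/9.71) = 3.3%.
- 120 h: 120/9.71 = 12.4 to 120/7.80 = 15.4 half-lives. The fraction left is at most 2^(−120/9.71) = 0.019%.

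**Weight of one substituted value**

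With 18 readings per treatment at 48 h, one value has weight 1/18 = 5.6%. If the true change is δ and the substitute shows none, the expected mean is (17/18)δ. That is an upper figure for the dilution. If the change has already gone by 48 h, the dilution is nil. The documents give no time course for vital signs or laboratory values, so the range per substitution is 0 to 5.6% of δ.

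**Which readings are exposed**

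Each meal state takes 9 of its 18 planned 48-h readings from Period 1, so both are equally open to the rule.

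**Where a Day 4-6 value could come from**

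Protocol 7.4 requires subjects terminated after dosing to have the Day 8 procedures. Suppose a subject leaves before 48 h and returns on Day 5. That subject gives vital signs and laboratory values with no row of their own in Table 2. If they are treated as unscheduled, they fall in the Day 3 window and fill the missing 48-h reading.

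**The case against.** The best defence is that no visit is scheduled on Days 4-6, so the wider range only gives stray values a home, and that Period 2 needs none because no scheduled visit follows Day 10. Subjects are also in the clinic until 48 h, so the Day 3 value will seldom be missing, and the value nearest Day 3 is preferred when there are several. Little drug remains at 48 h in any case. Sequence is randomized 1:1, no hypothesis is tested (SAP 3.3), and the PK parameters use actual elapsed times.

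All of this limits the size, and it stands. It does not justify the rule: giving a Day 6 value a place in a listing is reasonable, but using it as a 48-h measurement is not.

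Four stronger readings are tempting, and the documents do not support them.

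- **A pre-dose repeat ECG or vital sign would replace a missing 4-h reading.** Both time points share one day-wide window, and repeats are foreseen (Protocol 6.5.1: "The investigator may repeat the ECG to verify the results of the original result"). If the repeat were the last before dosing it would also be the baseline (SAP 6.3.6: "Baseline ECGs will be defined as the last evaluation performed prior to the administration of study drug in each treatment period"), and the change would be exactly zero. But filling is limited to the same nominal visit or time point, and pre-dose and 4 h are separate nominal time points. The SAP does not direct this substitution. It only prints no hour limits that would rule it out.
- **A delayed Period 2 would fall in the wrong windows.** The Protocol Synopsis says "A washout period of at least 7 days will be used between the two treatment periods", but the same Synopsis and the schedule place admission on Day 7 and dosing on Day 8. Scheduled Period 2 data keep their nominal labels whatever the date. Only unscheduled values in a delayed period could be misplaced, and only if study days run from the first dose, which SAP 6.1.1 does not state. On that assumption, with dosing on Day 10, an unscheduled dosing-day value would fall in the Day 10 window and Days 11-12 would have none.
- **The hepatic-enzyme repeat in Protocol 6.9.4.3 would trigger the rule.** It would not, because the Day 3 value that prompted the repeat exists, so nothing is missing.
- **The 3-6 window distorts ECG summaries.** No ECG is scheduled on Day 3, so there is no Period 1 48-h ECG to fill.

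**Conclusion.** The point holds for vital signs and laboratory tests at the 48-h visit. Table 2 and the fill-in rule together allow a Day 4-6 value to be reported as the 48-h value in Period 1, and give Period 2 no such allowance. This follows from the stated rule and does not depend on missing detail.

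It is minor. It acts only when the scheduled Day 3 value is missing and an unscheduled value exists on a later day of the window, which is probably rare. It reaches descriptive safety summaries only, and it does not systematically favour fed or fasted dosing. The figure of at most 5.6% of a mean change per substitution assumes 18 readings per treatment and a substitute that shows no change. The half-life argument assumes the protocol's range applies to this tablet in these subjects.

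**What to change.** In SAP Table 2, change the Day 3 window from 3-6 to 3, matching Day 10. State that values from Days 4-6 are listed but do not fill the 48-h time point.

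Two clarifications can go in while the table is open. Define study day, and count Period 2 windows from the actual second dose. State that only post-dose values can fill a post-dose time point.

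The washout wording should also be reconciled: the Protocol Synopsis sets a minimum of 7 days, while Protocol 3.3 describes a 7-day washout.

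The cost is one table, a sentence or two, and the matching programming. A few missing readings will stay missing, which agrees with the general rule in SAP 8.1 that missing data are kept as missing unless otherwise specified.
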